6.3.6 Overread service

For each HCP participating in the BiaB study, we offer an overread service that involves a group of specialists who can provide advice on the output and potential next steps if needed.

6.4 Withdrawal of individual patients

Patients will visit their HCP once for the BiaB study. Afterwards, patient reported outcomes will be collected using questionnaires. Patients can leave the study (stop answering questionnaires) at any time for any reason if they wish to do so without any consequences.

6.5 Replacement of individual patients after withdrawal

Patients that left the study will not be replaced.

6.6 Follow-up of patients withdrawn from study

There will be no follow-up of patients withdrawn from the study.

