4.3 Sample size determination

The sample size was determined to reliably demonstrate that there is a difference in the number of days between presentation with breathlessness in the clinic and diagnosis of a disease or disorder causing this breathlessness between usual care and the BiaB intervention.

For stepped-wedge clustered designs, the sample size is a combination of the number of clusters, the number of sequences, the number of time periods and the number of individuals per cluster period.⁷ Research shows that the best method of estimating the required sample size for a

stepped-wedge design is to simulate the power based on the method of analysis proposed including time in the chosen model.^{8,9} Therefore, for this study a sensitivity analysis has been performed using a desired power of 80% for the test of the intervention, with a type I (two-tailed) error rate of 0.05. The analysis was performed using the US National Institute for Health Stepped-wedge Group-Randomized Trials (SWGRT) Calculator software.¹⁰

The following assumptions were considered:

- The expected cluster autocorrelation (between two consecutive periods at the cluster level) was estimated 0.8, as healthcare professionals (HCPs) will use standard protocols or guidelines which are not expected to change between consecutive (6 week) periods within the study period.
- The intra class correlation was set to 0.03 based on previous data.¹¹
- The expected individual autocorrelation (between two consecutive periods at the level of the patient) was estimated 0.8, as HCPs will use standard protocols or guidelines which are not expected to change between consecutive (6 week) periods within the study period.
- The decay-structure for over-time correlations is Block-exchangeable.
- The churn rate was set to 0.0, as the study consists of one visit for data collection and data essential for the primary objective can be retrieved from HCPs.
- The number of patients per sequence (3 practices) is 60.
- Variation in cluster size is not taken into account as 60 patients will be included per cluster for analyses.
- The expected distribution of the primary outcome, dichotomous was set to 0.3.
- There are 6 time periods (including usual care and BiaB intervention period).

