6.1.1 Primary study endpoint

The primary endpoint is days between presentation with or consultation for breathlessness and a diagnosis causing the breathlessness (usual care group versus BiaB intervention group).

Required variables:

- Date of presentation with breathlessness,
- Date of first consultation for breathlessness,
- Date of diagnosis, and
- Type of diagnosis.

Strategy: Data will be retrieved during patient consultation (presentation and consultation for breathlessness) and periodically (up to 12 months, to account for referral waiting times) from healthcare professional (HCP) reporting (date and type of diagnosis). The exact date of presentation with breathlessness, consultation and diagnosis will be recorded. If exact date of presentation is unknown, it will be set to [01/MM/YYYY], where MM is the month where symptoms started. If duration of presentation is >1 month and start date is unknown, it will be set to either [01/01/YYYY] or [01/07/YYYY] (whichever is most accurate). Date of diagnosis is defined as date of recorded diagnosis related to breathlessness by any HCP (either reported by

HCP or noted in referral documentation) or start of treatment related to breathlessness. If multiple diagnoses are recorded, all will be collected, and the first diagnosis is used to determine time to diagnosis. Patients with missing data will be censored. In countries where a preliminary diagnosis is entered int the medical records to make prescription of medication possible before diagnostic tests are performed, the date of diagnosis will be validated by the HCP to ensure final clinical diagnosis date.

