6.3.3 HCP reported outcomes

During Visit 1 and the follow-up period, every three months for up to a year, HCPs will be asked to provide details on patient characteristics, medical information, diagnosis, medication, and referrals.

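### Sections 6.4 and 6.6, read literally, stop HCP-reported diagnosis data for a patient who chooses to stop questionnaires, although the sample size relies on those data remaining available

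*Protocol*

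**What the plan says.** Three short sections govern patients who leave.

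- Section 6.4: "Patients can leave the study (stop answering questionnaires) at any time for any reason". The parenthesis is the only description of leaving that the section gives.
- Section 6.5: "Patients that left the study will not be replaced".
- Section 6.6, in full: "There will be no follow-up of patients withdrawn from the study". It does not separate patient questionnaires from HCP-reported or record data.

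The primary endpoint uses a different data stream. Section 6.1.1 takes date and type of diagnosis from HCP reporting for up to 12 months. Section 6.3.3 sets the schedule: "During Visit 1 and the follow-up period, every three months for up to a year, HCPs will be asked to provide details", with diagnosis among the items. Section 6.1.1 also states "Patients with missing data will be censored".

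The sample size in 4.3 relies on that stream: "The churn rate was set to 0.0, as the study consists of one visit for data collection", and because "data essential for the primary objective can be retrieved from HCPs".

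**The concern.** The sample-size section argues that no primary-outcome data need be lost, because the HCP can supply them without the patient. The withdrawal sections, taken at their word, tell sites to stop collecting them once a patient gives up the questionnaires. Both cannot be applied to the same patient.

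The endpoint is a time to event with up to 12 months of observation. A patient who leaves undiagnosed would be censored then, although the practice will probably know later whether and when a diagnosis was made. Patients might stop because they have been diagnosed and feel better, or because they are still without an answer. Practices and patients know whether BiaB was used, so stopping could also differ between conditions. In either case the censoring could be informative.

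The first secondary endpoint is exposed too. Diagnoses made after the patient leaves would not be counted, and 6.1.2.1 records a patient with no reported diagnosis as a late diagnosis, whereas 6.1.1 censors a patient with missing data.

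This is a rule about data collection. An analysis plan cannot recover diagnosis dates that nobody was asked to report.

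**Working it through.** **Step 1. Follow one patient through the text.** The patient is enrolled, has no diagnosis at month 3, and tells the practice that he or she will answer no more questionnaires.

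| Section | Consequence on a literal reading |
|---|---|
| 6.4 | The patient has left the study |
| 6.5 | No replacement |
| 6.6 | No follow-up of any kind |
| 6.3.3 | HCP reports due at months 6, 9 and 12 fall in the follow-up period, so they lapse |
| 6.1.1 | Date of diagnosis missing; patient censored |
| 4.3 | Loss assumed to be zero because the HCP can supply the data |

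The last row conflicts with the rows above it.

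**Step 2. Reproduce the stated detectable difference.** Inputs from 4.3: ICC 0.03, cluster autocorrelation 0.8, individual autocorrelation 0.8, block-exchangeable correlation, T = 6 periods, 5 sequences, 60 patients per cluster, churn 0, power 80%, two-sided alpha 0.05. The stated figures are matched with I = 15 clusters (5 sequences in each of 3 countries), the same 60 patients measured in every period, and a t multiplier on 15 − 7 = 8 degrees of freedom. The closed-cohort reading and the degrees of freedom are inferred because they reproduce the figures; the protocol does not state them.

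With total variance 1 and m patients per cluster:

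- between-period variance of a cluster mean: s = 0.03 × 0.2 + (0.97 × 0.2)/m = 0.006 + 0.194/m
- shared variance: c = 0.03 × 0.8 + (0.97 × 0.8)/m = 0.024 + 0.776/m
- design sums, 3 clusters per sequence: U = 3(1+2+3+4+5) = 45; W = 9(1+4+9+16+25) = 495; V = 3(1+4+9+16+25) = 165
- Var = I·s·(s + T·c) / [(I·U − W)·s + (U² + I·T·U − T·W − I·V)·c] = 15·s·(s + 6c) / (180·s + 630·c)
- detectable difference = (2.3060 + 0.8889) × √Var = 3.1949 × √Var

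At m = 60: s = 0.009233, c = 0.036933, Var = 0.0012824, √Var = 0.03581, so the detectable difference is 3.1949 × 0.03581 = **0.1144**. With variance 0.1 this is 0.1144 × √0.1 = 0.0362. With binary variance (0.21 + 0.25)/2 = 0.23 it is 0.1144 × √0.23 = 0.0549. The protocol states 0.1144, 0.0362 and 0.055.

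**Step 3. Remove patients.** The protocol gives no withdrawal rate, so the rates below are assumptions. Each lost patient is taken to contribute nothing, which is a worst case.

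| Assumed loss | Patients left of 900 | m | s | c | √Var | Detectable, standardized | Absolute, binary |
|---|---|---|---|---|---|---|---|
| 0% | 900 | 60 | 0.009233 | 0.036933 | 0.03581 | 0.1144 | 0.0549 |
| 10% | 810 | 54 | 0.009593 | 0.038370 | 0.03650 | 0.1166 | 0.0559 |
| 20% | 720 | 48 | 0.010042 | 0.040167 | 0.03735 | 0.1193 | 0.0572 |
| 30% | 630 | 42 | 0.010619 | 0.042476 | 0.03840 | 0.1227 | 0.0588 |

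Even at 30% the detectable difference rises by a factor of only 0.1227/0.1144 = 1.07. The absolute figure of 0.0588 stays well below the hypothesized 0.2.

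**The case against.** The strongest reply is that the protocol can be read coherently. Section 6.4 speaks of patient-reported outcomes; HCP reporting has its own section and schedule (6.3.3); section 3 also plans extraction of electronic medical data from the practices before, during and at the end of the study. On that view, 6.6 means only that the patient is not contacted again. Section 9.2.1 provides separately for withdrawal of consent, where ending data collection is defensible. This reading is possible, and loss of the outcome is certain only on the literal one. But 6.6 does not say so, and 6.3.3 places HCP reports within the follow-up period that 6.6 ends. Forty-five practices in three countries could apply it differently.

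Four stronger conclusions that a reader might draw are not supported:

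- **That a missed or late questionnaire makes a patient withdrawn.** Section 6.4 describes a patient's choice to leave. It does not mention passive non-response.
- **That the primary comparison is biased in a known direction or by a known amount.** The protocol gives no withdrawal rate, no difference between conditions and no link to outcome. Informative censoring is a risk, not a finding.
- **That power suffers materially.** Larger figures (0.281 rising to 0.294, 0.310 and 0.329 SD at 10%, 20% and 30% loss) come from a cross-sectional model with 45 practices. That is a different baseline from the protocol's calculation and raises a separate question.
- **That censored patients drop out of the analysis.** They contribute time up to leaving, and an earlier diagnosis counts. If times were exponential (an assumption) with the planning means of 70 and 70 − 14 = 56 days, 1 − exp(−91/70) = 73% of usual-care and 1 − exp(−91/56) = 80% of BiaB patients would be diagnosed by day 91 after presentation, around the first follow-up questionnaire. Total loss is therefore an upper limit.

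**Conclusion.** The point holds as a conflict in the text. On the literal reading of 6.4 and 6.6, a patient who chooses to stop questionnaires also loses further collection of the HCP-reported diagnosis, which 6.1.1 and 6.3.3 schedule and on which 4.3 bases zero loss. The main cost is avoidable early censoring of the primary endpoint, which could be informative; its size and direction cannot be given from the protocol. The precision cost is small: at most 0.1144 to 0.1227 under an assumed 30% total loss, in the protocol's own model and conditional on the inferred closed-cohort structure and 8 degrees of freedom. If the sponsor intended the softer reading, no data need be lost and the zero-loss figures stand, but the text still has to say so. The change should be made.

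**What to change.** Reword 6.4 to 6.6, and the consent form to match:

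- State that stopping the questionnaires is not withdrawal from the study.
- Continue HCP-reported collection of diagnosis, referrals and events to 12 months for every enrolled patient, unless the patient withdraws consent to use of record data.
- Record the type of withdrawal (questionnaires only, or consent to record data) and its date.
- In 6.1.1, censor undiagnosed patients only at the date of withdrawal of consent to record data, or at the end of the 12-month HCP follow-up.

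The cost is a small change of wording in the protocol and consent form. No new procedure is needed, because HCP reporting is already quarterly for a year. The right to leave without consequences is kept, and patients gain a clear choice between ending questionnaires and ending use of their records.

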7. SAFETY REPORTING

7.1 Temporary halt for reasons of patient safety

In accordance with section 10, subsection 4, of the WMO, the sponsor will suspend the study if there is sufficient ground that continuation of the study will jeopardise patients health or safety. The sponsor will notify the accredited Institutional Review Board (IRB) without undue delay of a temporary halt including the reason for such an action. The study will be suspended pending a further positive decision by the accredited IRB. The investigator will take care that all patients are kept informed. The investigators perceive the occurrence of this risk as very low.

7.2 AEs, SAEs and SUSARs

7.2.1 Adverse events (AEs)

Since the current study is a quality improvement project only adverse events occurring while using BiaB will be considered and reported as (serious) adverse events. Adverse events occurring during the follow-up period of a patient will not be recorded or reported as such.

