A BiaB-app has been designed to create an efficient workflow and to guide the healthcare professional (HCP) through the diagnostic process, by instructing to perform several tests and subsequently providing automatic interpretation of the results. All test equipment (all CE marked) will be available in the BiaB-box (figure 3) and can be performed by an HCP following a consultation for breathlessness. The BiaB-procedures will take approximately 20 minutes in total (based on the pilot study) and require limited training as all separate tests and the BiaB-application (BiaB-app) have been designed with usability in mind. During a BiaB visit, the entire box with all its tests will be conducted, except for the D-dimer test and YEARS criteria, which will be administered only if pulmonary embolism is suspected.

Clinical history

General characteristics of the patient are collected in the BiaB-app, including gender, age, height, weight, duration of dyspnea symptoms, and whether pulmonary embolism (PE) is suspected.

These characteristics are necessary input for the BiaB-algorithm to provide an accurate result.

The following tests are included:

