5.1.4 YEARS criteria and D-dimer test

Sudden breathlessness may be a sign of pulmonary embolism (PE), which requires urgent care. Therefore, it is important to investigate further when PE is suspected. This is a common method in primary care. This can be done using the YEARS criteria, which are derived from the most predictive items of the previously used Wells score. Compared to the Wells scores, with fixed D-dimer cut off values, the YEARS algorithm reduces the use of a CT pulmonary angiogram (CTPA) by 14%. The YEARS algorithm has been shown to rule out PE (only 0.43% with a symptomatic venous thromboembolism (VTE) during 3 months follow-up) and has been incorporated in international guidelines. The score derived from the YEARS algorithm dictates interpretation of the D-dimer test. D-Dimer, a fibrin degradation product, is a thrombotic biomarker used to exclude PE.²⁷

In cases of suspicion of a PE, the YEARS criteria (Appendix A) and a D-dimer test will be advised in the BiaB-app. D-dimer can be tested on the same LumiraDx point-of-care device used to measure NT-proBNP levels with a different test cartridge. The measurement will be performed in approximately 10 μ L of capillary blood obtained by a standard finger stick. PE can be ruled out if none of the YEARS items are applicable and D-dimer <1000 ng, or, if 1-3 YEARS items are applicable and D-dimer is <500 ng (Figure 6). 25,26

[figure not shown]

Figure 6. Decision tree for YEARS algorithm with binary d-dimer cut off values, adapted from Van der Pol 2019²⁸.

Results generated by the LumiraDx will be retrieved by the BiaB-app automatically. The BiaB-app will interpret the measurement according to guidelines taking into account the relevant dependencies. Results will be incorporated into the BiaB-report.

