6.1.2.2 Second secondary endpoint

The second secondary endpoint is to demonstrate the usability and efficiency of BiaB.

Required variables:

- Number of lung function tests
- Number of ECG measurements
- Number of referrals to specialist
- Type of referral to specialist
- Number of acute hospital admissions
- Duration of hospital admission
- Number of emergency room visits

Strategy: Data will be retrieved from HCP reported outcomes. Anonymous data pertaining to the total number of lung function tests, ECG measurements and referrals are not limited to patients participating in the BiaB study.

- Clinical outcomes
 - o Contents of BiaB report
 - a) Test results
 - b) Outcomes
 - c) Advice
 - d) Diagnosis
 - o Change in breathlessness³⁰
 - Number of cardiopulmonary events ³¹
 - a) COPD exacerbation
 - b) Myocardial infarction
 - c) Stroke
 - d) Heart failure decompensation
 - e) Arrhythmia
 - f) Death due to any of these events
 - o Change in prescribed medication

Performed procedures (at visit and follow-up/referral)

Strategy: Change in breathlessness will be measured over time (0, 3, 6, 9, 12 months) as a patient reported outcome using the numeric rating scale (NRS)^{32,33}. The number of cardiopulmonary events will be recorded at 3, 6, 9, 12 months, reported by HCP. Cardiopulmonary events are defined as COPD exacerbation, myocardial infarction, stroke, heart failure hospitalization, arrhythmia, and death due to any of these events³¹. COPD exacerbations are identified through use of oral corticosteroids irrespective of antibiotics use. Arrhythmia is defined as atrial and ventricular tachyarrhythmia. Change in prescribed medication will be determined by comparing medication prescribed before consultation for breathlessness to prescribed medication after consultation for breathlessness as reported by HCP. Data about procedures performed during visit, follow-up and referral will be collected through HCP reported outcomes.

BiaB use

- Number of times BiaB is started
- Number of unique generated reports
- State of generated reports
- Number of times BiaB advice is followed
- Prescribed treatment or referrals
- Performed procedures

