7.2.2 Serious adverse events (SAEs)

A serious adverse event is any untoward medical occurrence or effect that:

- results in death;
- is life threatening (at the time of the event);
- requires hospitalisation or prolongation of existing inpatients' hospitalisation;
- results in persistent or significant disability or incapacity;
- is a congenital anomaly or birth defect; or
- any other important medical event that did not result in any of the outcomes listed above due to medical or surgical intervention but could have been based upon appropriate judgement by the investigator.

An elective hospital admission will not be considered as a serious adverse event.

Only SAEs occurring during or directly after the use of the BiaB-box will be considered and reported as SAEs.

The investigator will report all SAEs to the National coordinator without undue delay after obtaining knowledge of the events, except for the following SAEs:

• Events related to the indication of the HCP consultation and not related to the procedures performed with the BiaB-box, as interpreted by the HCP.

The National coordinator will report the SAEs through the national applicable way to the accredited IRB that approved the protocol, within 7 days of first knowledge for SAEs that result in death or are life threatening followed by a period of maximum of 8 days to complete the initial preliminary report. All other SAEs will be reported in line listings after study closure.

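### A pulmonary embolism missed after a BiaB rule-out is not captured as a safety event, and PE/VTE is absent from the follow-up cardiopulmonary event list

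*Protocol*

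**What the plan says.** **Rule-out function.** Protocol section 5.1.4 uses the YEARS items with a point-of-care D-dimer: "PE can be ruled out if none of the YEARS items are applicable and D-dimer <1000 ng", with a second condition for patients who have one or more items. The app interprets the result and places it in the BiaB-report. The list of definitions makes receipt of that report part of the BiaB-procedure. Section 5 restricts YEARS and D-dimer to a subgroup, "which will be administered only if pulmonary embolism is suspected".

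**Evidence cited.** Section 5.1.4 supports the rule-out with "only 0.43% with a symptomatic venous thromboembolism (VTE) during 3 months follow-up".

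**Safety recording.** Section 7.2.1 says that "only adverse events occurring while using BiaB will be considered and reported as (serious) adverse events", and continues: "Adverse events occurring during the follow-up period of a patient will not be recorded or reported as such". Section 7.2.2 allows SAEs at the time of box use or straight afterwards. It exempts from reporting: "Events related to the indication of the HCP consultation and not related to the procedures performed with the BiaB-box, as interpreted by the HCP".

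**Follow-up events.** Section 6.1.2.2 has HCPs report cardiopulmonary events at 3, 6, 9 and 12 months: "Cardiopulmonary events are defined as COPD exacerbation, myocardial infarction, stroke, heart failure hospitalization, arrhythmia, and death due to any of these" events. PE and VTE are not among them.

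**The concern.** The trial asks whether diagnosis becomes faster. The harm that goes with a faster answer is a wrong answer, and for a rule-out pathway that means a patient who has the excluded condition. This harm does not show at the visit. It shows over the following weeks, and the protocol's own citation uses a three-month window.

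The safety section closes before that window opens. The follow-up event list covers the window but leaves out the condition. Each choice might be defended alone. Together they mean that no planned safety or clinical-event output names the outcome on which the rule-out claim rests. The study could report its cardiopulmonary events and its BiaB-related SAEs in full, as the protocol requires, and neither would show a PE that emerged weeks after a report had excluded it.

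**Working it through.** **1. Could a later PE count in each planned output?** Take a BiaB patient whose report rules out PE and who has a symptomatic PE six weeks later.

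| Output | Section | Captured? |
|---|---|---|
| Adverse event | 7.2.1 | No; it falls in follow-up |
| Serious adverse event | 7.2.2 | No; six weeks is not during or straight after use |
| Cardiopulmonary event | 6.1.2.2 | No; PE/VTE is not listed |
| Cardiopulmonary death | 6.1.2.2 | No; only deaths from listed events count |
| Diagnosis record | 6.1.1, 6.1.2.1, 6.3.3 | Yes, as one diagnosis among all types, to 12 months |
| Acute admission, emergency visit | 6.1.2.2 | Yes, as a count under usability and efficiency |
| Mortality, complications | 6.1.2.2, economic analysis | Yes, as HCP-reported input to costs |

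The first four rows are the safety and clinical-event outputs, and none captures it. The last three can hold it, but for other purposes. For the first secondary endpoint, diagnoses are grouped as heart, respiratory, psychological or other, so PE would not be separately visible there.

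**2. Number of BiaB patients.** Section 3 gives 45 sites and 20 patients per site: 45 × 20 = 900, which agrees with the stated total. At the intended 1:1 ratio, 900 / 2 = 450 are in the BiaB group.

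**3. Expected missed events.** The 0.43% comes from a cited study. Its numerator and denominator are not in the protocol, so it cannot be reproduced here and is taken as given. The share of BiaB patients who will be ruled out is not stated, so a range is assumed. Expected events = n × 0.0043; chance of at least one = 1 − 0.9957^n.

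| Assumed share ruled out | n | Expected events | Chance of at least one |
|---|---|---|---|
| 5% | 22 | 0.09 | 9% |
| 10% | 45 | 0.19 | 18% |
| 20% | 90 | 0.39 | 32% |
| 30% | 135 | 0.58 | 44% |
| 100% (ceiling only) | 450 | 1.94 | 86% |

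The last row is an arithmetic ceiling. It cannot occur as planned, because the tests are limited to suspected PE.

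**4. What zero events would show.** With no events, the one-sided 95% upper bound is 1 − 0.05^(1/n): 6.4% for n = 45 and 2.2% for n = 135. These are about 15 and 5 times the cited 0.43% (6.4 / 0.43 = 14.9; 2.2 / 0.43 = 5.1). The trial cannot confirm the cited rate or compare rates between periods. It can identify and describe individual cases.

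**The case against.** The strongest reply is that the data will exist. Section 6.1.1 collects every diagnosis with its date for up to 12 months, including diagnoses after the first. HCPs report quarterly (6.3.3), and patients complete quarterly diagnosis and healthcare-use questionnaires (6.3.2). Admissions, emergency visits, mortality and complications are all recorded. The contents of the BiaB-report are kept, and section 6.1.2.2 plans to compare its advice with later referrals, procedures, diagnoses and treatment. The report also carries a link through which a specialist can enter the diagnosis (6.3.4).

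This reply stands against three stronger readings that a reader might infer:

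- **That a missed PE cannot surface at all.** It can, as a diagnosis, an admission, an emergency visit or a death.
- **That it could never be linked to the report.** Both items are collected for the same patient. However, the planned comparison serves to count how often advice was followed; it does not flag a diagnosis that contradicts a rule-out.
- **That the negligible-risk statement in section 9.3 is made true by the recording rules.** That statement is prospective. It rests on the tests being non-invasive and validated, not on event counts from this trial.

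Two further points count for the protocol. PE work-up is described as common in primary care, so the risk is not peculiar to BiaB. The SAE exemption requires an event to be both related to the indication and unrelated to the procedures. Since the procedure includes receiving the report, harm from a wrong report is arguably not exempt. The main limit is the time window, not the exemption.

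The reply does not remove the omission of PE/VTE from the defined event list. It also does not turn diagnosis or cost data into a planned account of this harm. Incidental capture depends on someone deciding to look for it.

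**Conclusion.** The point holds as a gap in ascertainment. A PE or PE death emerging in the weeks after a BiaB rule-out is not an adverse event, not an SAE and not a cardiopulmonary event under the protocol, and could be found only incidentally in data gathered for other purposes.

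The expected number is small: about 0.2 to 0.6 events at an assumed 10-30% ruled out, with an 18-44% chance of at least one. This rests on about 450 BiaB patients, on the assumed share, and on the cited 0.43% carrying over to this box and setting. That figure is symptomatic VTE in another study, not a miss rate observed with BiaB. The argument for change therefore rests on identifying individual cases, not on statistical precision. It should be corrected because the remedy is cheap and specific, but it does not threaten the primary analysis.

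**What to change.** In section 6.1.2.2:

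1. Add symptomatic PE/VTE, and death due to it, as HCP-reported events at 3, 6, 9 and 12 months. Collect them identically for usual-care and BiaB patients. If the existing composite should stay as in its cited source, report them on a separate line.
2. List each such event in the BiaB group against that patient's YEARS/D-dimer result in the BiaB-report, or record that these were not done.

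The cost is one extra item on a form that HCPs already complete every quarter, and one short listing. Because section 6.6 gives no follow-up after withdrawal, the listing should state how many BiaB patients were not followed for the full three months.

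Extending SAE reporting to later events contradicting a report is not part of this recommendation. It would apply to BiaB patients only, so ascertainment would differ between periods. That choice is best left to the sponsor. Nothing here alters how patients are tested or managed.
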